**Table 3.1.2-1: Guidance for Safety Monitoring Based on Observed Toxicity Outcomes**

Number of participants treated and followed up for at least 6 weeks after start of study treatment	Number of participants with DLTs	Next Step
9	≤ 2	Tolerable
9	≥ 3	To be discussed between sponsor and investigators to review benefit/risk ratio

The duration of the study is anticipated to be approximately 2 years. The end of the trial will occur on the day of the last visit of the last participant.

### **3.1.3 Part 2**

#### **3.1.3.1 Mismatch Repair/Microsatellite Instability Testing**

##### **MSI testing**

Microsatellite instability - high is most frequently determined by polymerase chain reaction (PCR). MSI-H in tumors refers to changes in two or more of the five microsatellite markers in tumor tissue identified by National Cancer Institute (NCI)-recommended panels. The original Bethesda guidelines (1997) proposed a panel of five microsatellite markers for the uniform analysis of MSI in hereditary non-polyposis colorectal cancer (HNPCC). This panel, which is referred to as the Bethesda panel, included two mononucleotide (BAT-25 and BAT-26) and three dinucleotide (D5S346, D2S123, and D17S250) repeats. Individual testing sites may utilize a slightly different panel of markers incorporating alternative mononucleotide and/or dinucleotide markers. Regardless of the panel of markers, samples with instability in ≥ 30% or more of these markers

are defined as MSI-H, whereas those with < 30% unstable markers are designated as MSI-Low (MSI-L). Samples with no detectable alterations are MSS.

### **MMR testing**

DNA mismatch repair deficiency determined by immunohistochemistry (IHC) refers to the loss of expression of one or more of the mismatch repair proteins (MLH1, MSH2, MSH6, or PMS2). Loss of expression is restricted to tumor cells, with preserved expression in immune infiltrate, and normal adjacent tissue. Loss of MLH1 expression is usually accompanied by loss of PMS2, and loss of MSH2 is usually accompanied by the loss of MSH6 expression.

In Part 2, participants with MSI-H/dMMR status determined prior to screening by local testing as part of the standard of care assessment can be eligible to the study. Please refer to [Appendix 4](#) regarding MSI/MMR testing panel descriptions and classification of MSI/MMR status to ensure historical MSI/MMR status determination is aligned with the protocol requirements prior to enrollment.

#### **3.1.3.2 Screening**

A complete schedule of activities for screening can be found in [Table 5.1-1](#).

Before Protocol Amendment 07, enrollment had stopped.

- Begins by establishing the participant's initial eligibility and signing of the informed consent form (ICF).
- Inclusion/Exclusion criteria are assessed during the screening period and must be confirmed prior to first dose
- All medical history relevant to the disease under study should be collected.
- Tumor tissue obtained from primary or metastatic site of disease.
  - Sufficient tumor tissue obtained before start of study treatment in the primary or metastatic sites (block or minimum of 10 slides, obtained from core biopsy, punch biopsy, excisional biopsy, or surgical specimen) will be submitted to the central laboratory.
  - For participants where a fresh biopsy is not feasible, archival tumor material are required.
  - An additional source of tumor tissue must be available if the tissue obtained adhering to the above guidelines cannot be tested due to poor quality or insufficient quantity.
  - Central lab must confirm receipt of evaluable tumor tissue prior to vial assignment for MSI/MMR testing (see [Section 5.6.2](#)).
- Prior to screening, medical record documentation of MSI/MMR testing results must be available. Related pathology reports must be available. Reports must contain MSI/MMR status results, and specific results per markers tested for MSI/MMR are also required if available.
- Collect RAS and BRAF mutation status, if available. Tests for these alterations are expected to be already performed for Arm D participants.
- Eligibility and baseline assessments should be performed within required timeframe according to [Table 5.1-1](#). The screening phase either ends with confirmation of full eligibility and treatment assignment for the participant or with the confirmation that the participant is a screen failure.

### **3.1.3.3    *Review of Safety***

The participants' safety will be monitored on an ongoing basis as described fully in [Section 6](#). In addition, a BMS medical safety team (MST) routinely reviews safety signals across the entire nivolumab program including combination studies with ipilimumab.

### **3.1.4    *Intra-Subject Dose Reductions***

Intra-subject dose reduction is not permitted for any reason. Dose delays for the management of study treatment-related AEs are described in [Section 4.5.3](#).

### **3.1.5    *Follow-Up***

Follow-up begins when the decision to discontinue a participant from study therapy is made (no further treatment with study therapy).

Participants will be followed for drug-related toxicities until these toxicities resolve, return to baseline, or are deemed irreversible up to follow-up visit 2 (FU2) or 100 days of study drug discontinuation, whichever occurs later. All AEs occurring within 100 days after last dose will be documented.

Tumor assessments for Arm D will continue until FU2 or 100 days after last dose, whichever is later.

Refer to [Table 5.1-5](#), [Table 5.1-6](#), and [Table 5.1-7](#) for additional follow-up assessments.

## **3.2    *Post Study Access to Therapy***

At the conclusion of the study, participants who continue to demonstrate clinical benefit will be eligible to receive BMS supplied study treatment for the maximum treatment duration of 2 years specified in protocol [Section 3.1.1](#). Study treatment will be provided via an extension of the study, a rollover study requiring approval by responsible health authority and ethics committee, or through another mechanism at the discretion of BMS. BMS reserves the right to terminate access to BMS supplied study treatment if any of the following occur: a) the study is terminated due to safety concerns; b) the development of nivolumab and/or ipilimumab is terminated for other reasons, including but not limited to lack of efficacy and/or not meeting the study objectives; c) the participant can obtain medication from a government sponsored or private health program. In all cases BMS will follow local regulations.

## **3.3    *Study Population***

For entry into the study, the following criteria MUST be met prior to dosing on Day 1. No exceptions will be granted. As of 20-Dec-2021, enrollment into this study Part 2 was closed.

### **3.3.1    *Inclusion Criteria***

#### **1) Signed Written Informed Consent**

- a) Participants must have signed and dated an IRB/IEC approved written informed consent form in accordance with regulatory and institutional guidelines. This must be obtained

before the performance of any protocol related procedures that are not part of normal participant care.

b) Participants must be willing and able to comply with scheduled visits (including overnight stays), treatment schedule, laboratory tests and other requirements of the study.

## 2) Target Population

a) Chinese participants with advanced or recurrent solid tumors

- i) histologically confirmed
  - (1) All CRC participants must be histologically confirmed metastatic or recurrent, with historically documented MSI-H or dMMR status by local testing (please refer to [Appendix 4](#) for definition of MSI-H/dMMR and panel to be used by local testing).
  - ii) must have failed at least one prior systemic chemotherapy for advanced disease, OR, well documented refusal of participants to receive chemo or biological therapy
    - (1) SCLC participant must have failed at least one prior systemic therapy for advanced disease including one platinum based regimen.
  - iii) must have at least 1 measurable lesion per Response Evaluation Criteria in Solid Tumors (RECIST 1.1) ([Appendix 1](#)).
  - (1) GC participants must have at least one measurable lesion or evaluable disease by computed tomography (CT) or magnetic resonance imaging (MRI) per RECIST 1.1 criteria.
  - (2) Participants with lesions in a previously irradiated field as the sole site of measurable disease will be permitted to enroll provided the lesion(s) have demonstrated clear progression and can be measured accurately.
- b) Eastern Cooperative Oncology Group Performance Status of 0 or 1 ([Appendix 2](#)).
- c) Life expectancy  $\geq$  3 months.
- d) Not applicable per Protocol Amendment 04.
- e) Not applicable per Protocol Amendment 04.
- f) Not applicable per Protocol Amendment 04.
- g) Not applicable per Protocol Amendment 04.
- h) Not applicable per Protocol Amendment 04.
  - i) Not applicable per Protocol Amendment 04.
  - ii) Not applicable per Protocol Amendment 04.
  - iii) Not applicable per Protocol Amendment 04.
  - iv) Not applicable per Protocol Amendment 04.
  - v) Not applicable per Protocol Amendment 04.
  - vi) Not applicable per Protocol Amendment 04.
  - vii) Not applicable per Protocol Amendment 04.

- viii) Not applicable per Protocol Amendment 04.
- i) Participant Re-enrollment: This study permits the re-enrollment of a participant that has discontinued the study as a pre-treatment failure (ie, participant has not been treated). If re-enrolled, the participant must be re-consented. Obtain agreement from the Medical Monitor prior to re-enrolling a participant.

## **Additional Criteria for Participants Enrolled in Part 2**

- j) Participants must have shown progression during, after, or have been intolerant to  $\geq 1$  line treatment(s) for metastatic disease, which must include at least a fluoropyrimidine, and oxaliplatin or irinotecan (participants who receive oxaliplatin in an adjuvant setting should have progressed during or within 6 months of completion of adjuvant therapy in order for oxaliplatin to count as a prior therapy needed for entry).
- k) Participant willing to comply to provide tumor tissue (archival or fresh biopsy specimen) (see [Section 5.6.2](#) for additional details regarding the requirements for tumor tissue).

### **3) Age and Reproductive Status**

Investigators shall counsel women of child-bearing potential (WOCBP) on the importance of pregnancy prevention, the implications of an unexpected pregnancy, and the potential of fetal toxicity occurring due to transmission of study drug to a developing fetus.

- a) Female Participants
  - i) Females ages 18 years, or age of majority, or older at time of consent
  - ii) Women who are not of childbearing potential are exempt from contraceptive requirements
  - iii) Women participants must have documented proof that they are not of childbearing potential.
  - iv) WOCBP must have a negative serum or urine pregnancy test (minimum sensitivity 25 IU/L or equivalent units of human chorionic gonadotropin) within 24 hours prior to the start of study treatment. An extension up to 72 hours prior to the start of study treatment is permissible in situations where results cannot be obtained within the standard 24-hour window.
  - v) Additional requirements for pregnancy testing during and after study intervention are located in [Section 5](#), Schedule of Assessments.
  - vi) The investigator is responsible for review of medical history, menstrual history, and recent sexual activity to decrease the risk for inclusion of a woman with an early undetected pregnancy
  - vii) WOCBP must agree to follow instructions for method(s) of contraception defined in [Appendix 5](#) and as described below and included in the ICF.
  - viii) WOCBP are permitted to use hormonal contraception methods (as described in [Appendix 5](#))
  - ix) A female participant is eligible to participate if she is not pregnant or breastfeeding, and at least one of the following conditions applies:

- (1) Is not a WOCBP
- OR
- (2) Is a WOCBP and using a contraceptive method that is highly effective (with a failure rate of < 1% per year), with low user dependency, as described in [Appendix 5](#) during the intervention period and for at least 5 months and agrees not to donate eggs (ova, oocytes) for the purpose of reproduction for the same time period
- b) Male Participants
  - i) Males, ages 18 years, or age of majority, or older at time of consent

### **3.3.2     *Exclusion Criteria***

#### **1. Target Disease Exceptions**

- a) Participants with untreated symptomatic central nervous system (CNS) metastases are excluded. Participants are eligible if CNS metastases are adequately treated and participants are neurologically returned to baseline (except for residual signs or symptoms related to the CNS treatment) for at least 2 weeks prior to enrollment. In addition, participants must be either off corticosteroids, or on a stable or decreasing dose of  $\leq 10$  mg daily prednisone (or equivalent). Imaging performed within 28 days prior to treatment assignment must document radiographic stability of CNS lesions and be performed after completion of any CNS directed therapy.
- b) Participants with leptomeningeal metastases.

#### **2. Medical History and Concurrent Diseases**

- a) Participants with previous malignancies or concurrent malignancies (present during screening) requiring treatment (except non-melanoma skin cancers, and the following in situ cancers: bladder, gastric, colon, endometrial, cervical/dysplasia, melanoma, or breast) are excluded unless a complete remission was achieved at least 2 years prior to study start AND no additional therapy is required or anticipated to be required during the study period.
- b) Participants with active, known or suspected autoimmune disease. Participants with vitiligo, type I diabetes mellitus, residual hypothyroidism due to autoimmune thyroiditis only requiring hormone replacement are permitted to enroll.
- c) Not applicable per Protocol Amendment 04.
- d) Active Tuberculosis (TB) infection based on chest X-ray, sputum tests, and clinical examination. Participants with a history of active TB infection within the last 1 year are excluded, even if it was treated. Participants with a history of active TB infection greater than 1 year ago are excluded unless there is documentation of adequate prior anti-TB treatment.
- e) Not applicable per Protocol Amendment 04.
- f) Not applicable per Protocol Amendment 04.
- g) Not applicable per Protocol Amendment 04.
- h) Not applicable per Protocol Amendment 04.
- i) Not applicable per Protocol Amendment 04.

- j) Not applicable per Protocol Amendment 04.
- k) Any other sound medical, psychiatric and/or social reason as determined by the investigator.
- l) Participants with interstitial lung disease that is symptomatic or may interfere with the detection or management of suspected drug-related pulmonary toxicity.
- m) Participants with a condition requiring systemic treatment with either corticosteroids (> 10 mg daily prednisone equivalent) or other immunosuppressive medications within 14 days of start of study treatment. Inhaled or topical steroids, and adrenal replacement steroid doses > 10 mg daily prednisone equivalent, are permitted in the absence of active autoimmune disease.
- n) Not applicable per Protocol Amendment 04.
- o) All toxicities attributed to prior anti-cancer therapy other than alopecia and fatigue (which can be Grade 2) must have been resolved to  $\leq$  Grade 1, or returned to baseline, or stabilized before administration of study drug. Participants with toxicities attributed to prior anti-cancer therapy which are not expected to resolve to Grade 1 and result in long lasting sequelae, such as neuropathy after platinum based therapy, are permitted to enroll.
- p) Any serious or uncontrolled medical disorder that, in the opinion of the investigator, may increase the risk associated with study participation or study drug administration, impair the ability of the participant to receive protocol therapy, or interfere with the interpretation of study result.
- q) Women who are of childbearing potential or breastfeeding

### **3. Physical and Laboratory Test Findings**

- a) Not applicable per Protocol Amendment 04.
- b) Not applicable per Protocol Amendment 04.
- c) Not applicable per Protocol Amendment 04.
- d) WBC  $< 2000/\mu\text{L}$
- e) Neutrophils  $< 1500/\mu\text{L}$
- f) Platelets  $< 100 \times 10^3/\mu\text{L}$
- g) Hemoglobin  $< 9.0 \text{ g/dL}$
- h) Serum creatinine  $> 1.5 \times \text{ULN}$ , unless creatinine clearance  $\geq 40 \text{ mL/min}$  (measured or calculated using the Cockcroft-Gault formula):

$$\text{Female CrCl} = (140 - \text{age in years}) \times \text{weight in kg} \times 0.85$$

$$72 \times \text{serum creatinine in mg/dL}$$

$$\text{Male CrCl} = (140 - \text{age in years}) \times \text{weight in kg} \times 1.00$$

$$72 \times \text{serum creatinine in mg/dL}$$

- i) AST:  $> 3.0 \times \text{ULN}$
- j) ALT:  $> 3.0 \times \text{ULN}$

- k) Bilirubin  $> 1.5 \times$  ULN (except participants with Gilbert Syndrome who must have total bilirubin  $< 3.0 \times$  ULN)
- l) Any positive test result for hepatitis B virus (HBV) indicating presence of virus, eg, Hepatitis B surface antigen (Australia antigen) positive.  
Any positive test result for hepatitis C virus (HCV) indicating presence of active viral replication (detectable HCV-ribonucleic acid [RNA]). Note: Participants with positive HCV antibody and an undetectable HCV-RNA are eligible to enroll.
- m) Positive blood screen for human immunodeficiency virus (HIV)-1, or -2 antibody.

#### 4. Allergies and Adverse Drug Reaction

- a) History of allergy or hypersensitivity to study drug components

#### 5. Other Exclusion Criteria

- a) Prisoners or participants who are involuntarily incarcerated. (Note: under certain specific circumstances a person who has been imprisoned may be included or permitted to continue as a participant. Strict conditions apply and BMS approval is required).
- b) Participants who are compulsorily detained for treatment of either a psychiatric or physical (eg, infectious disease) illness
- c) Inability to comply with restrictions and prohibited activities/treatments as listed in [Section 3.4](#)

#### 6. Prior /Concomitant Therapy

- a) Prior treatment with an anti-PD-1, anti-PD-L1, anti-PD-L2, anti-CTLA-4 antibody, or any other antibody or drug specifically targeting T-cell co-stimulation or immune checkpoint pathways, including prior therapy with anti-tumor vaccines or other immuno-stimulatory antitumor agents
- b) Treatment with any chemotherapy, curative intent radiation therapy, biologics for cancer, or investigational therapy must have been completed at least 28 days before first administration of study treatment. Prior focal palliative radiotherapy must have been completed at least 2 weeks before study drug administration. Participants with prior cytotoxic or investigational products  $< 4$  weeks prior to treatment might be eligible after discussion between investigator and sponsor, if toxicities from the prior treatment have been resolved to  $\leq$ Grade 1 (NCI Common Terminology Criteria for Adverse Events [CTCAE] version 4.0) or returned to baseline.
- c) Participants who have received a live / attenuated vaccine within 30 days of first treatment
- d) Prior major surgery requiring general anesthesia must be completed at least 2 weeks before study drug administration. Surgery requiring regional/epidural anesthesia must be completed at least 72 hours before study drug administration and participants must be recovered. Cutaneous biopsies with only local anesthesia should be completed at least 1 hour prior to study drug administration.
- e) Any use of immunosuppressive systemic medications, such as steroids (dose  $> 10$  mg/day prednisone or equivalent) within 2 weeks of study drug administration.
- f) Any use of traditional medicinal herbal preparations within 2 weeks of study drug administration.

Eligibility criteria for this study have been carefully considered to ensure the safety of the study participants and that the results of the study can be used. It is imperative that participants fully meet all eligibility criteria.

### **3.3.3      *Women of Childbearing Potential***

See [Appendix 5](#).

## **3.4          *Concomitant Treatments***

### **3.4.1       *Prohibited and/or Restricted Treatments***

The following medications and treatments are prohibited during the study (unless utilized to treat a drug-related adverse event):

- Immunosuppressive agents
- Immunosuppressive doses of systemic corticosteroids. Participants are permitted the use of topical, ocular, intra-articular, intranasal, and inhalational corticosteroids (with minimal systemic absorption). Adrenal replacement steroid doses  $> 10$  mg daily prednisone are permitted. A brief (less than 3 weeks) course of corticosteroids for prophylaxis (eg, contrast dye allergy) or for treatment of non-autoimmune conditions (eg, delayed-type hypersensitivity reaction caused by a contact allergen) is permitted.
- Any concurrent systemic anti-neoplastic therapy (ie, chemotherapy, hormonal therapy, immunotherapy, or standard or investigational agents for treatment of CRC)
- Any non-palliative radiation therapy. Radiation therapy administered with palliative intent (ie, for pain, bleeding, spinal cord compression, brain metastasis, new or impending pathologic fracture, superior vena-cava syndrome, or obstruction) is permitted.
- Any complementary medications (eg, herbal supplements or traditional Chinese medicines) intended to treat the disease under study. Such medications are permitted if they are used as supportive care.
- Any live / attenuated vaccine (eg, varicella; zoster; yellow fever; rotavirus; oral polio; and measles, mumps, rubella) during treatment and until 100 days post last dose.
  - COVID-19 vaccines that are NOT live are allowed and should be handled in the same manner as other vaccines. Administration may occur during the study, including during the administration of the BMS study treatment and after the last administration of the BMS study treatment. Non-live COVID-19 vaccination is considered a simple concomitant medication within the study. However, the efficacy and safety of non-live vaccines (including non-live COVID-19 vaccines) in participants receiving nivolumab and/or ipilimumab are unknown.

### **3.4.2       *Other Restrictions and Precautions***

Participants are permitted the use of topical, ocular, intra-articular, intranasal and inhalational corticosteroids (with minimal systemic absorption). Physiologic replacement doses of systemic corticosteroids (ie, prednisone  $\leq 10$  mg/day) are permitted. A brief course of corticosteroids for prophylaxis (eg, contrast dye allergy) or for treatment of non-autoimmune conditions (eg, delayed-

type hypersensitivity reaction caused by a contact allergen) or for management of study drug-induced adverse events are permitted.

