#### **4.5.5 Criteria to Resume Treatment**

Participants may resume study treatment when the drug-related AE(s) resolve(s) to Grade  $\leq$  1 or baseline, with the following exceptions:

- Participants may resume treatment in the presence of Grade 2 fatigue.
- Participants who have not experienced a Grade 3 drug-related skin AE may resume treatment in the presence of Grade 2 skin toxicity.
- For participants with Grade 2 AST, ALT and/or Total Bilirubin Abnormalities, dosing may resume when laboratory values return to baseline and management with corticosteroids, if needed, is complete. Participants with baseline Grade 1 AST/ALT or total bilirubin elevations who require dose delays for reasons other than a 2-grade shift in AST/ALT or total bilirubin may resume treatment in the presence of Grade 2 AST/ALT OR total bilirubin.
- Participants with isolated AST/ALT elevations or combined with total bilirubin elevations meeting discontinuation parameters ([Section 4.5.6](#)) should have treatment permanently discontinued, except situations outlined in the [Section 4.5.6](#).
- Drug-related pulmonary toxicity, diarrhea, or colitis must have resolved to baseline before treatment is resumed. Participants with persistent Grade 1 pneumonitis after completion of a steroid taper over at least 1 month may be eligible for retreatment if discussed with and approved by the BMS Medical Monitor.
- Drug-related endocrinopathies adequately controlled with only physiologic hormone replacement may resume treatment after consultation with the BMS Medical Monitor. If participant experienced Grade 3 adrenal insufficiency study treatment should not be resumed regardless of control with hormone replacement.

Participants with SARS-CoV-2 infection (either confirmed or suspected) may resume treatment after all of the following conditions are met:

- At least 10 days (20 days for severe/critical illness) have passed since symptoms first appeared or positive test result (eg, reverse transcription polymerase chain reaction or viral antigen)
- Resolution of acute symptoms (including at least 24 hours has passed since last fever without fever reducing medications)
- Evaluation by the investigator with confirmation that there are no sequelae that would place the participant at a higher risk of receiving investigational treatment.

For suspected cases, treatment may also resume if SARS-CoV-2 infection is ruled out and other criteria to resume treatment are met.

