  - Grade 4 drug-related endocrinopathy adverse events such as hyper- or hypothyroidism, or glucose intolerance, which resolve or are adequately controlled with physiologic hormone replacement (corticosteroids, thyroid hormones) or glucose controlling agents, respectively, may not require discontinuation after discussion with and approval from the BMS Medical Monitor
- Dosing delays lasting  $>$  6 weeks for Q2W dosing (nivolumab monotherapy) or  $>$  8 weeks for Q3W dosing (nivolumab combined with ipilimumab) from the previous dose requires discontinuation. The following exceptions apply:
  - Dosing delays to allow for prolonged steroid tapers to manage drug-related adverse events are allowed.
  - Dosing delays lasting  $>$  6 weeks from the previous dose that occur for non-drug-related reasons may be allowed if approved by the BMS medical monitor.
- Any adverse event, laboratory abnormality, or intercurrent illness which, in the judgment of the Investigator, presents a substantial clinical risk to the participant with continued nivolumab dosing.

Prior to re-initiating treatment in a participant with a dosing delay lasting  $>$  6 weeks, the BMS medical monitor must be consulted. Tumor assessments should continue as per protocol even if dosing is delayed. Periodic study visits to assess safety and laboratory studies should also continue every 6 weeks or more frequently if clinically indicated during such dosing delays.

The assessment for discontinuation of ipilimumab should be made separately from the assessment made for discontinuation of nivolumab. Although there is an overlap among the discontinuation criteria, if discontinuation criteria are met for ipilimumab but not for nivolumab, treatment with nivolumab may continue if ipilimumab is discontinued.

If a participant meets the criteria for discontinuation of ipilimumab but not nivolumab, treatment with nivolumab may not resume until the AE/SAE has fully resolved and the participant has discontinued steroids, if they were required for treatment of the AE/SAE. The relationship to ipilimumab should be well documented in the source documents. Nivolumab should be resumed at the dose according to the treatment schedule ([Table 5.1-2](#), [Table 5.1-3](#) and [Table 5.1-4](#)).

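### Section 3.4.2 is out of step with other current text on the steroid replacement dose and on the length of steroid courses for drug-induced adverse events

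*Combined protocol and SAP*

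**What the plan says.** Four current sections of the protocol bear on systemic steroids during the study.

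- **Section 3.4.1** lists treatments that are "prohibited during the study (unless utilized to treat a drug-related adverse event"; the exemption has no time limit. It also allows "A brief (less than 3 weeks) course of corticosteroids for prophylaxis" or for non-autoimmune conditions, and it permits adrenal replacement above 10 mg of prednisone daily.
- **Section 3.4.2** covers the same ground again. It permits "Physiologic replacement doses of systemic corticosteroids (ie, prednisone" at or below 10 mg/day). It also has the sentence beginning "A brief course of corticosteroids for prophylaxis (eg, contrast dye allergy", which lacks the 3-week figure and has a further use added at the end: "or for management of study drug-induced adverse events are permitted".
- **Section 4.5.5** considers retreatment of a participant whose Grade 1 pneumonitis persists "after completion of a steroid taper over at least 1 month", with the medical monitor's approval. It also lets a participant with a drug-related endocrinopathy resume, after consulting the medical monitor, if physiologic hormone replacement alone controls it.
- **Section 4.5.6** states: "Dosing delays to allow for prolonged steroid tapers to manage drug-related adverse events are allowed". It exempts Grade 3 endocrinopathies from discontinuation when physiologic replacement alone controls them. It has a similar Grade 4 exemption, subject to the medical monitor's approval, which names corticosteroids among the replacement hormones. Grade 3 adrenal insufficiency ends treatment whatever the replacement.

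At entry, exclusion 2m in section 3.3.2 says: "Inhaled or topical steroids, and adrenal replacement steroid doses > 10 mg daily prednisone equivalent, are permitted in the absence of active autoimmune disease". Exclusion 6e bars systemic steroids above 10 mg/day within 2 weeks of study drug and gives no replacement exception.

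**The concern.** Appendix 3 makes corticosteroids a primary therapy for immune-related toxicity, so sites apply these rules when participants are unwell. Section 3.4.2 sets a different replacement dose from 3.4.1. It also puts toxicity treatment under a *brief* course, where other sections allow long ones.

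The dose figure matters because of where the word *physiologic* is used. It decides whether a participant with an endocrinopathy may resume or stay on treatment. If sites take the meaning from different sections, similar participants can leave treatment at one site and continue at another. The count of adverse events leading to discontinuation, a primary endpoint in Part 1, would then partly reflect which section a site relied on.

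**Working it through.** The plan gives no figure to reproduce. The check sets the passages side by side, with simple arithmetic.

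**1. Replacement dose.** Section 3.4.1 permits more than 10 mg/day; 3.4.2 permits 10 mg/day or less. The two ranges share no value. Read as permissions, together they cover every dose. If 3.4.2 is read as a limit, it rules out what 3.4.1 permits.

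**2. Where the dose has consequences.** Sections 4.5.5 and 4.5.6 state no dose in mg, so they contradict neither section directly. They rely on the word *physiologic*, which only 3.4.2 quantifies. Take a participant with a drug-related endocrinopathy, other than Grade 3 adrenal insufficiency, controlled on steroid replacement:

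| Replacement dose | Site relying on 3.4.1 | Site using the 3.4.2 figure as the definition |
|---|---|---|
| 10 mg/day or less | Exceptions in 4.5.5 and 4.5.6 available | Same |
| Above 10 mg/day | Dose permitted; site may regard it as physiologic, so exceptions available | Not physiologic, so exceptions not available |

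In the lower right cell the general rules return. Under 4.5.5 the event must fall to Grade 1 or baseline before dosing resumes. Under 4.5.6 a Grade 3 non-skin event lasting more than 7 days ends treatment.

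**3. Duration.** Section 3.4.2 does not define *brief*. The 3-week figure in 3.4.1 applies only to prophylaxis and non-autoimmune conditions.
- Assume that *brief* in 3.4.2 carries that figure. Then the course is under 21 days, while a taper of at least 1 month is at least 28 to 31 days. The gap is at least 28 − 21 = 7 days, and the two do not overlap.
- Without that assumption the mismatch is verbal: *brief* in 3.4.2 against *prolonged* in 4.5.6 for the same use. The 4.5.6 exception comes into play only when the interval since the previous dose exceeds 6 weeks (nivolumab every 2 weeks) or 8 weeks (combination every 3 weeks), although the taper itself need not last that long.

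Sections 3.4.1, 4.5.5 and 4.5.6 agree with each other on duration. Only 3.4.2 stands apart.

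**4. Entry criteria.** Exclusion 2m (14 days before treatment) permits adrenal replacement above 10 mg/day. Exclusion 6e (2 weeks before study drug) can be read to exclude it. The windows are equal and the outcome can be opposite. Part 2 enrollment closed on 20 December 2021 and all 36 participants have been treated, so no entry decision now depends on this.

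**5. Size.** Each arm has 9 treated participants. One participant discontinued under one reading and retained under the other changes that arm's rate by 1/9 = 11.1 percentage points. The documents give no count of participants on replacement above 10 mg/day.

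**The case against.** The best reply is that every sentence at issue in 3.4.2 is a permission. None sets a maximum, and the only prohibition, in 3.4.1, exempts treatment of drug-related events. Read together, the texts allow all the uses described. Section 4.5.6 then settles long tapers expressly, and 4.5.8 sends sites to the Appendix 3 algorithms, whose detail is in figures that are not shown here.

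Much of this stands for duration. It does not settle the dose point. Permission to give a dose does not say whether that dose is *physiologic* under 4.5.5 and 4.5.6, and 3.4.2 introduces its figure as a definition. The medical monitor's role helps only partly. Consultation or approval is required to resume, or to keep a Grade 4 case on treatment. A site that decides the exception is unavailable, and stops, is not told to consult.

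A reader might infer more than the documents support:

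- *That all four sections contradict each other.* Section 3.4.1 does not conflict with 4.5.5 or 4.5.6 on duration, and those two give no dose.
- *That sites would cut tapers short.* A site would have to set aside the 3.4.1 exemption and 4.5.6.
- *That participants would be withdrawn under 3.5 for inability to comply with the protocol.* This route is conceivable but not shown. Neither 3.5 nor 4.5.6 makes the length of a steroid course a reason to discontinue.
- *That 2 to 3 participants per arm are affected.* This takes the 29.7% with endocrine select adverse events in section 1.4.4.4 (0.297 × 9 = 2.7). That figure covers all drug-related endocrine select events, not those needing steroid replacement. It comes from melanoma studies of nivolumab 1 mg/kg plus ipilimumab 3 mg/kg, which matches only Arm C's induction.

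**Conclusion.** The point holds in a limited form. Section 3.4.2 differs from 3.4.1 on the replacement dose. Through the word *physiologic*, that difference can change whether a participant with a drug-related endocrinopathy resumes or stays on treatment. Grade 3 adrenal insufficiency is outside the problem. On duration, 3.4.2 is worded out of line with the other three sections, but no effect on retention is shown.

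The dose conclusion assumes that a site would use the figure in 3.4.2 to interpret 4.5.5 and 4.5.6. That is reasonable, because the protocol offers no other figure for the term, but no text requires it. The 7-day gap in duration assumes that *brief* carries the 3-week meaning across from 3.4.1.

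An effect on adverse events leading to discontinuation is plausible but unquantified; 11.1 points is the size of one participant in an arm, not an estimate. The mismatch between exclusions 2m and 6e now matters only for classifying protocol deviations. The point has no bearing on the sample size or on the analysis of response.

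**What to change.** The sponsor should reconcile 3.4.1, 3.4.2, 4.5.5 and 4.5.6. Three uses each need one consistent statement: prophylactic and non-autoimmune courses, treatment of drug-related adverse events, and adrenal replacement. The word *physiologic* should have one meaning wherever resumption or discontinuation depends on it.

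Simply deleting the overlapping text in 3.4.2 is not advised. It would settle the clinical question in favor of 3.4.1 without a medical decision. The sponsor's medical team should decide the content; no dose or duration is proposed here.

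For reporting, the sponsor should also state how exclusions 2m and 6e are read together when protocol deviations are classified.

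The cost is protocol wording, with no added procedures or data.
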